If a patient opts out of sharing their anonymised data for research purposes with UoM (Appendix 1, Screenshot 6), we will withdraw their data. When a patient has used PATCHS it is impractical to find out whether they subsequently lose capacity as all registered patients at the GP practices can use PATCHS. If a GP practice staff member uses PATCHS then subsequently loses capacity, we will continue to use the data they provided before losing capacity. If data have already been extracted, we will be unable to withdraw participants' data because the data will have been anonymised and we will be unable to identify the participant.

9) OUTCOME MEASURES

Primary outcome measure

Our primary outcome measure is the proportion of delays in completing urgent and emergency online consultations at the patient-level:

(delayed urgent online consultations + delayed emergency online consultations)

- ÷ (total urgent patient online consultations
- + total emergency online consultations)

It was chosen because patients and clinicians we consulted during our PPI work felt it was the most clinically important outcome measure. Delays will be measured by the difference between the date-time that an urgent or emergency online consultation was submitted by a patient in PATCHS and the date-time the consultation was completed in PATCHS by GP practice staff. Based on our PPI work, we will consider an urgent online consultation delayed if it is not completed within 48 hours and an emergency online consultation delayed if it is not completed within 24 hours. Online consultations that have not yet been completed but were submitted by patients more than 48 hours previously at the point of data extraction will be included. In intervention practices we define online consultations as urgent or emergency where a GP practice staff member has applied a triage decision as either 'urgent' or 'emergency', or where AI Triage predicts an online consultation as 'urgent' or 'emergency' which is unchanged by staff. We will assume that patients who receive a signpost message and cancel their online consultation will have sought care from other services and not experienced a care delay. In control practices we define online consultations as urgent and emergency only if GP practice staff apply a triage decision as either 'urgent' or 'emergency'.

Secondary outcome measures

Interrupted Time Series Analysis

Patient-level - binary

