 Proportion of delayed emergency online consultations at the patient-level (disaggregated primary outcome measure; denominator=number of emergency online consultations)

- Proportion of delayed urgent online consultations at the patient-level (disaggregated primary outcome measure; denominator=number of urgent online consultations)
- Proportion of online consultations cancelled by patients at the patient-level (denominator=number of online consultations)
- Proportion of online consultations assigned to clinicians (denominator=total number of online consultations)

Patient-level – continuous

- Absolute time to completion for urgent and emergency online consultations (combined and separate)
- Absolute time to completion for routine online consultations
- Absolute time to first staff user action in online consultation system for urgent and emergency online consultations (combined and separate)
- Absolute time to first staff user action in online consultation system for routine online consultations

GP practice-level – counts (workload measures)

- Proportion of total appointments provided by GP practices (denominator=GP practice population size
 (1))
- Proportion of online consultations submitted by patients (denominator= GP practice population size)
- Proportion of patients with emergency department attendances (denominator=GP practice population size (37))
- Proportion of online consultations with emergency department attendances (denominator=total number of online consultations (37))
- Proportion of patients with emergency hospital admissions (denominator=GP practice population size (37))
- Proportion of online consultations with emergency hospital admissions (denominator=total number of online consultations (37))

GP practice-level – continuous (cost measures)

- Cost of clinicians processing online consultations within the GP practice per 1000 patients
- Cost of emergency department attendances and emergency hospital admissions per 1000 patients

Quantitative process evaluation

For readability, these are described in more detail in the statistical analysis section.

- Fidelity, dose, and reach of Al Triage and online consultations
- Al Triage accuracy, true positive rate, true negative rate, positive predictive value, and negative
 predictive value for predicting urgent and emergency online consultations (combined and separate)
 in intervention GP practices
- Potential triage behaviour change in control GP practices

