11.1 Statistical Analysis

Interrupted Time Series Analysis

Design

Each intervention GP practice will be matched one-to-one with a control practice according to the characteristics described above. At least 12 months of outcome data before, and following, the index date will be available for analysis.

[figure not shown]
Descriptive statistics

Characteristics of intervention and control practices and their patients, and those that crossed over or declined the intervention, in terms of variables used for matching and all outcome measures, will be compared descriptively and inferentially in the pre-intervention period using t-tests for continuous and Fisher's exact tests for categorical variables. Outcome measures will be plotted as monthly time series of events across the pre- and intervention periods.

Modelling

To analyse binary patient-level outcomes, including our primary outcome measure (proportion of delayed urgent and emergency online consultations; proportion of delayed urgent online consultations; proportion of delayed emergency online consultations; proportion of online consultations cancelled by patients; proportion of online consultations assigned to clinicians), we will use mixed-effects logistic regression models with appropriate offset terms (number of urgent and emergency online consultations). We will initially analyse data as a time series with a minimum of 12 time points (months) pre-intervention and 12 intervention. The main exposure of interest will be membership to the intervention or control group modelled as binary (0/1). Models will be adjusted for practice characteristics that we have been unable to match during randomisation described elsewhere (e.g. patient population size). Where possible, we will also adjust models for the following practice characteristics that may influence the primary outcome measure: length of time using PATCHS without AI Triage, and other features enabled in PATCHS (the system has several configurable features such as different AI modules). Time will be modelled as continuous (1 to 24) to account for trends in the pre-intervention period. We will also attempt to include month as a categorical variable to account for seasonality. The main parameter of interest will be the interaction term between practice group (intervention vs control) and study period (pre- vs intervention); post-estimation commands will be used to obtain estimates for each study period by practice group.

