To analyse continuous patient-level outcome measures (absolute time to completion or staff user action for urgent and emergency online consultations – combined and separate; absolute time to completion or staff user action for routine online consultations) we will use mixed-effects linear regression models with all other aspects of the analysis remaining the same.

If multiple online consultations are submitted by the same patient, we will randomly sample one per patient for analysis. Multiple online consultations from the same patient are expected to be infrequent, though if this approach adversely affects reaching our sample size target we will instead include all online consultations with a patient-level variable in our models.

To analyse count GP practice-level outcome measures (proportion of total appointments provided by GP practices; proportion of online consultations submitted by patients; proportion of patients with emergency department attendances; proportion of online consultations with emergency department attendances; proportion of patients with emergency hospital admissions; proportion of online consultations with emergency hospital admissions) we will use negative binomial regression models with appropriate offset terms for the denominators. For example, GP practice population size (40) or number of whole-time equivalent GPs per 1000 patients (39).

[figure not shown]

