Limitations with the above approach include that: staff triage decisions could be applied by non-clinicians which could be systematically different to those applied by clinicians (43); we assume that patients who receive a signpost message and cancel their online consultation have not experienced a care delay; and the triage decisions made by GP practice staff may be highly variable. We will therefore conduct sensitivity analyses where: we restrict triage decisions to those only made by clinicians; we exclude patients who receive a signpost message and cancel their online consultation; we define online consultations as urgent and emergency in intervention and control practices if they are predicted as either 'urgent' or 'emergency' by Al Triage. We will also conduct sensitivity analyses where we sub-sample practices and patients with similar: baseline levels of the outcome measure, monthly volume of online consultations per 1000 patients, prevalence of urgent and emergency online consultations, agreement with AI Triage predictions, contributions to AI Triage model training, and other variables matched during randomisation and model adjustment where appropriate. Further sensitivity analyses may be undertaken based on findings from the process evaluation (44), for example, we may find a cohort of practices that did not engage with the Al Triage training, and we may test the hypothesis that Al Triage was less effective at reducing delays in urgent and emergency online consultations for them. We will also explore using an alternative analysis approach, interacting practice group with time and period to estimate the adjusted intervention time series. For example, a difference-in-difference method pooling the outcome (and the offset) in the preand intervention periods.

Health inequalities

We will use the pre-intervention period to assess for inequalities in the influence of patient characteristics on experiencing urgent and emergency care delays in both the pre- and intervention periods. We will use

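### The primary logistic model names the count of urgent and emergency consultations as an offset: redundant or misnamed at best, and biasing if log counts per practice-month are fitted and AI Triage changes flagging

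*Protocol*

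**What the plan says.** Section 9 defines the primary outcome at the level of the consultation: "Our primary outcome measure is the proportion of delays in completing urgent and emergency online consultations at the patient-level". Its denominator is urgent plus emergency consultations. Membership of that denominator is defined differently by arm. In intervention practices a form counts if staff flag it, "or where AI Triage predicts an online consultation as 'urgent' or 'emergency' which is unchanged by staff". For controls, "In control practices we define online consultations as urgent and emergency only if GP practice staff apply a triage decision" of one of those two kinds.

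For the primary and four other binary outcomes, section 11.1 (Modelling) says: "we will use mixed-effects logistic regression models with appropriate offset terms (number of urgent and emergency online consultations". On the effect measure it says: "The main parameter of interest will be the interaction term between practice group (intervention vs control) and study period (pre- vs intervention".

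Three other places bear on the point:

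- Section 9 gives other outcomes in the same list other denominators, for example "Proportion of online consultations cancelled by patients at the patient-level (denominator=number of online consultations".
- For the continuous patient-level outcomes, section 11.1 says "we will use mixed-effects linear regression models with all other aspects of the analysis remaining the same".
- Under Sensitivity analyses, section 11.1 mentions "a difference-in-difference method pooling the outcome (and the offset" as one alternative to be explored.

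For the practice-level counts, section 11.1 uses negative binomial models with offsets for the denominators. That is the standard use.

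**The concern.** An offset enters the linear predictor with its coefficient fixed at 1. In a log-link count model, log(denominator) as offset turns a count into a rate. On the logit scale the same term does something else: it makes the odds of delay proportional to the denominator. A practice-month with twice as many flagged forms is then modelled as having twice the odds of delay, before any other term acts. The denominator has already done its work as the number of binomial trials, or through the number of rows.

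This would matter little if the count could not respond to the intervention. Here it can. AI Triage pre-populates the triage decision (section 7.2), an AI flag left unchanged counts in intervention practices only, and the process evaluation plans to track urgent and emergency decision counts in both arms. If a log-count offset is fitted, any change in flagging specific to the AI arm passes into the group-by-period coefficient, which is the primary effect. More flags would look like fewer delays, and fewer flags like more.

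**Working it through.** **Inputs from the protocol.** Section 11.2 gives baseline delay of 25%, target 20%, 90% power, 5% alpha, 50 flagged forms per practice-month, and 20 + 20 practices. Section 11.1 gives 12 + 12 months and the group-by-period interaction as the effect.

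**Input not in the protocol.** k, the pre-to-intervention ratio of flagged volume in AI practices divided by the same ratio in controls. All values of k below are assumed.

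**1. The plan's own figure.** Two proportions, two-sided, pooled variance, no continuity correction:

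n per arm = [1.960·√(2 × 0.225 × 0.775) + 1.2816·√(0.25 × 0.75 + 0.20 × 0.80)]² / 0.05² = (1.1575 + 0.7555)² / 0.0025 ≈ 1464, so 2928 in total. The stated figure is reproduced. It does not involve the offset.

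**2. Target effect as an odds ratio.** (0.20/0.80) / (0.25/0.75) = 0.75.

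**3. Effect of a log(n) offset.** The model is logit(p) = log(n) + Xβ, so Xβ describes logit(p) − log(n). Taking the difference between periods and then between arms:

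interaction = log(true OR) − log(k), so fitted OR = true OR / k.

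A change in volume common to both arms is absorbed by the period term; only the differential change k remains. With no true effect, the apparent delay is (OR/3) / (1 + OR/3), since the baseline odds are 1/3:

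| Assumed k | Fitted OR, no true effect | Apparent change from 25% |
|---|---|---|
| 0.80 | 1.25 | to 29.4% |
| 1.10 | 0.91 | to 23.3% |
| 1.25 | 0.80 | to 21.1% |
| 1.33 | 0.75 | to 20.0% (the target) |
| 1.50 | 0.67 | to 18.2% |

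In the other direction, a true fall to 20% with k = 0.75 gives 0.75/0.75 = 1.00, and the benefit disappears.

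**4. Simulation check.** Practice-month binomial data, 20 + 20 practices, 24 months, mean 50 forms a month, assumed between-practice variance 0.1 (one of the values in Table 1), practice fixed effects standing in for random intercepts, 100 runs per setting:

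| Setting | OR with log(n) offset (rejected) | OR without offset (rejected) |
|---|---|---|
| No effect, k = 1 | 1.00 (9%) | 1.00 (8%) |
| No effect, k = 1.10 | 0.91 (58%) | 1.00 (1%) |
| No effect, k = 1.25 | 0.80 (100%) | 1.00 (2%) |
| No effect, k = 1.50 | 0.67 (100%) | 1.00 (4%) |
| True 25% to 20%, k = 1 | 0.75 (100%) | 0.75 (100%) |
| True 25% to 20%, k = 0.75 | 0.99 (8%) | 0.75 (100%) |

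With 100 runs the standard error of a 5% rejection rate is √(0.05 × 0.95/100) = 2.2 points, so the 1% to 8% seen under no effect without the offset is compatible with 5%. When flagging does not shift (k = 1), the offset does no visible harm to the interaction.

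**5. Other ways of fitting it.** With the raw count as offset, each extra form moves the log-odds by one unit: a rise from 50 to 55 in AI practices alone shifts the interaction by about −5. With one row per consultation and an offset of log(1) = 0, the term does nothing. With one row per consultation carrying the practice-month count, step 3 applies again.

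**6. Does the named count fit the listed outcomes?**

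| Outcome in the sentence | Section 9 denominator | Same as named count? |
|---|---|---|
| Delayed, urgent and emergency | urgent + emergency | yes |
| Delayed, urgent | urgent only | no |
| Delayed, emergency | emergency only | no |
| Cancelled by patient | all online consultations | no |
| Assigned to clinicians | all online consultations | no |

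**The case against.** The strongest reply is that the damaging model is inferred. The protocol does not say log(n), does not give the scale of the offset and does not define the rows. Much of the text points to one row per consultation: patient-level binary outcomes, consultation-level data, and sampling of one consultation per patient. The count in parentheses is exactly the primary denominator, so the authors may be using the word loosely for the number of trials. Either way no bias arises. This stands, and it makes the numerical result conditional. It does not rescue the sentence. The same section also speaks of a monthly time series and of pooling the offset, so aggregated fitting remains open, and the loose reading supplies the wrong denominator for four of five outcomes unless the parenthesis is only an example for the primary.

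There are partial safeguards. The process evaluation would reveal a shift in flagging, and one sensitivity analysis defines urgency by AI prediction in both arms. Neither protects the primary estimate.

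Four stronger readings are tempting and not supported:

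- That the primary result will be biased. This needs both a log or raw count in the predictor and k different from 1.
- That AI Triage is known to raise flag volume. Tuning for a high true positive rate makes a rise plausible, but staff can upgrade or downgrade, and the protocol gives neither size nor direction.
- That offsets never belong in logistic models. They can be used there; the objection is to the denominator as offset.
- That the linear models carry an offset. The carry-over phrase permits that inference but names none.

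**Conclusion.** The point holds in conditional form. As written, the offset in the primary logistic model is redundant or misnamed at best. If log(n) per practice-month is fitted, the interaction odds ratio is multiplied by 1/k without any change in delay, and a one-third relative rise in flags is enough to imitate the whole design effect. A raw-count offset would be worse. The size rests on an assumed k and on a scale and row structure that the protocol leaves open. The mismatch with section 9 for the other four binary outcomes does not depend on k. Because this is the primary model, and section 4 (Issue 4) commits to reporting departures from the protocol as such, the text should be corrected before analysis rather than silently reinterpreted.

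**What to change.** - In section 11.1, delete the offset from the logistic models. Either fit one row per consultation, or fit practice-month events/trials using each outcome's own section 9 denominator.
- Keep offsets for the negative binomial count models only.
- In the sensitivity analyses, align the reference to pooling the offset, for example by pooling events and trials.
- State that the carry-over phrase for the linear models does not bring an offset with it.

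The cost is a few lines of text before analysis. No extra data are needed and the sample size of 2928 is unaffected. The change does not address a shift in the case-mix of flagged forms between arms, which is a separate question.

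### The logistic models, including the primary one, are specified with the consultation count as an offset; entered literally, any relative change in flagged volume would shift the treatment effect

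*Protocol*

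**What the plan says.** Protocol section 11.1 (Modelling) puts five binary patient-level outcomes, the primary one among them, into "mixed-effects logistic regression models with appropriate offset terms (number of urgent and emergency online consultations"). The list also contains "proportion of online consultations cancelled by patients; proportion of online consultations assigned to clinicians".

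The data are monthly: "We will initially analyse data as a time series with a minimum of 12 time points (months) pre-intervention and 12 intervention". The estimand is a two-way contrast: "The main parameter of interest will be the interaction term between practice group (intervention vs control) and study period (pre- vs intervention"). Under Sensitivity analyses in the same section, the alternative difference-in-difference approach is described as "pooling the outcome (and the offset) in the preand intervention periods", so the offset is treated as a quantity that belongs to a period.

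The models for continuous patient-level outcomes are linear and otherwise inherit the same specification. The practice-level counts go into negative binomial models with offsets for the denominators. The examples given are: "For example, GP practice population size (40) or number of whole-time equivalent GPs per 1000 patients (39").

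Section 9 gives each outcome its own denominator, for instance "Proportion of online consultations assigned to clinicians (denominator=total number of online consultations"). It also defines the flagged consultations differently by arm. In intervention practices a consultation counts if staff flagged it, "or where AI Triage predicts an online consultation as 'urgent' or 'emergency' which is unchanged by staff". In control practices only staff flags count.

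**The concern.** An offset is a term whose coefficient is fixed at 1. In a count model, log(denominator) as offset turns a count into a rate. In a logistic model the denominator is already in the likelihood, so an added log(N) does not normalise anything. It asserts that the odds of delay rise in direct proportion to the number of consultations flagged.

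This matters because the number flagged may move in exactly the cell that the interaction isolates: intervention practices after AI Triage is switched on. The arm-specific definition in section 9 makes such a move plausible. So do the automatic pre-filling of triage flags (section 7.2) and the tuning of the AI towards sensitivity (section 5). The model would then report the change in volume as a change in delay.

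There is also a governance cost. Section 4 (Issue 4) relies on pre-registration, with departures reported as such, to manage a declared commercial interest. Following the wording risks a distorted estimate. Departing from it silently weakens that safeguard.

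**Working it through.** **1. The plan's own figure.** Inputs from section 11.2: p1 = 0.25, p2 = 0.20, 90% power, 5% alpha (taken as two-sided).

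n per arm = [1.960·√(2·0.225·0.775) + 1.282·√(0.25·0.75 + 0.20·0.80)]² / 0.05² = [1.960·0.5906 + 1.282·0.5895]² / 0.0025 ≈ 1464

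The total is 2 × 1464 = 2928, as stated. With 50 consultations per practice-month, 1464 / (50 × 12) = 2.44, so three practices per arm, also as stated. The sample size does not involve the offset and is unaffected.

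**2. Target effect as an odds ratio.** (0.20/0.80) / (0.25/0.75) = 0.75.

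**3. Effect of a log(N) offset.** The model is logit(p) = log(N) + η, so η = logit(p) − log(N). The interaction is the difference in differences of η:

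interaction = true log OR − log(k), where k = (N intervention, after / N intervention, before) / (N control, after / N control, before)

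The fitted odds ratio is therefore the true odds ratio divided by k. The value of k that imitates the target effect under no true effect is 1/0.75 = 1.33, that is, 50 rising to about 67 flagged consultations per practice-month.

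If the offset is constant within a practice, it cancels between periods and is absorbed by the practice intercept, so nothing is biased.

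**4. Simulation under no effect on delay.** Set-up: 20 + 20 practices, 12 + 12 months, a mean of about 50 flagged per practice-month, 25% delay throughout and practice-intercept SD 0.3. The binomial logit model had practice intercepts (fixed, standing in for random), period, linear time and group × period. There were 40 runs per scenario, so rejection shares are rough. The values of k are assumptions.

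| k | 1/k | OR, log(N) by practice-month | Implied delay from 25% | Runs with p < 0.05 | OR, no offset | OR, offset constant per practice |
|---|---|---|---|---|---|---|
| 0.8 | 1.25 | 1.25 | 29.4% | 40/40 | 0.99 | 1.01 |
| 1.0 | 1.00 | 0.99 | 24.9% | 2/40 | 1.00 | 1.01 |
| 1.1 | 0.91 | 0.91 | 23.3% | 23/40 | 1.00 | 1.00 |
| 1.2 | 0.83 | 0.83 | 21.7% | 40/40 | 1.00 | 1.00 |
| 1.33 | 0.75 | 0.75 | 20.1% | 40/40 | 1.01 | 1.00 |
| 1.5 | 0.67 | 0.66 | 18.1% | 40/40 | 1.01 | 1.01 |
| 2.0 | 0.50 | 0.51 | 14.5% | 40/40 | 1.00 | 1.01 |

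The simulated values follow 1/k in both directions.

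**5. Denominators side by side.** The bracketed count is the section 9 denominator of the primary outcome. The separate urgent and emergency outcomes have their own, narrower denominators. The cancelled and clinician-assigned outcomes have all online consultations as denominator. Whole-time-equivalent GPs per 1000 patients, offered as an example offset for the count models, is the denominator of no section 9 outcome.

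**The case against.** The best defence is that the word is loose. The bracketed quantity is the primary outcome's denominator, the count-model paragraph uses offsets to stand for denominators, and pooling the outcome and the offset reads naturally as pooling numerators and denominators. Patient-level outcomes and the sampling of one consultation per patient also imply individual records. If the analysts simply supply trials or 0/1 records, there is no bias. The protocol never mentions a log scale. Exact coding may also be settled in an analysis plan that is not shown.

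Much of this stands, and it makes the bias conditional. It does not rescue the sentence. The protocol names a logistic model and names an offset for it, nowhere equates the two ideas, and attaches the offset to a period.

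A reader might infer more than the documents support, in three ways:

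- **That the plan is tilted in favour of AI because raising flags is its purpose.** The protocol describes tuning for sensitivity and assisting triage. It lets staff downgrade AI flags and forecasts no change in volume. A fall would bias against AI (k = 0.8, odds ratio 1.25).
- **That the wrong denominator is definitely assigned to the cancelled and clinician-assigned outcomes.** The wording is plural and says the terms will be appropriate, so the bracket may name only the primary outcome's. That is an ambiguity to clear up.
- **That the GP workforce example adds to the problem with the primary outcome.** It is an example, for secondary count models, and has no bearing on it.

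The sensitivity analysis that defines urgency by AI prediction in both arms would largely remove a flagging difference, but it leaves the primary model as written.

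**Conclusion.** The offset is wrong for a logistic model and should be removed. The potential size is a multiplication of the interaction odds ratio by about 1/k. A relative rise of one third in flagged volume would by itself reproduce the whole target effect (0.75), a rise of 20% gives about 0.83, and a fall of 20% gives about 1.25.

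This rests on three conditions: the offset is entered literally, it is on the log scale, and it varies by month or period. The monthly series and the pooling by period point to the third. The first two are not settled by the text. All values of k are illustrative. The documents do not show that a false reduction in delays will occur, only that the stated model would produce one if flagged volume rose and the wording were followed.

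**What to change.** In section 11.1:

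- Delete the offset from the logistic models and from the patient-level linear models that inherit it.
- State that the binary outcomes are analysed as one record per consultation, or as events/trials with each outcome's own section 9 denominator (all online consultations for cancelled and for assigned to clinicians).
- Keep log-denominator offsets only in the negative binomial models, using the section 9 denominators. Do not use GP workforce as an offset.
- Amend the difference-in-difference sentence to speak of pooling events and denominators.

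The cost is a few lines of wording, with no change to sample size, data collection or conduct. It is best done as a dated amendment before the interrupted time series data are transferred.

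This does not cure the separate problem that section 9 defines flagged consultations differently in the two arms, which can change the case mix behind the proportion itself and needs its own treatment.
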